### **X. Data Safety Monitoring Plan**

This project seeks to test the efficacy of the Caregiver Speaks intervention and explore how caregivers' making meaning of their caregiving and bereavement experiences affects their grief intensity. To our knowledge, this is the first hospice intervention offered during active caregiving, following caregivers into bereavement that utilizes the innovative storytelling technique of photo-elicitation. The study will occur in geographically separate hospice programs across the Missouri and in Pennsylvania. The study will use block randomization, with block sizes randomly varying between 6 and 10 to randomize participants into control and Intervention groups, making group allocation difficult to discern. The Data Manager will prepare sequentially numbered, opaque envelopes using a computer to generate random numbers. The total sample will be 468 hospice family caregivers of PLWD in Missouri and Pennsylvania. Participants will be at least 18 years of age, meet the study's inclusion criteria and provide consent to participate. The sample will be referred by hospice admissions staff following a consent-to-contact discussion with the caregiver. Participants in the usual care group will receive traditional hospice care and will be asked questions from the instruments upon enrollment, and every 30 days up to 180 days bereaved. We will conduct a follow-up transition interview with the family caregivers in for the intervention group only at 14-21 days following death of their loved one, then again at ~100-110 days bereaved (for intervention group only). Participants in the Caregiver Speaks intervention group will receive the same measures in addition to the following: participation in a secret Facebook group and facilitated photo-elicitation storytelling intervention. As part of

overseeing the Facebook group's psychosocial concerns, Co-investigator [name] will contact any participant reporting thoughts or actions of harming themselves or others via the Facebook discussion and initiate the participant safety plan.

The Co-Principal Investigators (Drs. [name] and [name]) and Data Manager ([name]) will be responsible for monitoring the safety and efficacy of this trial, executing the Data and Safety Monitoring plan, and complying with the reporting requirements. The PIs will provide a summary of the report to the National Institute on Aging (NIA) annually as part of the progress report. The Data and Safety Monitoring report will include participants' socio-demographic characteristics, expected-versus-actual recruitment rates, retention rates, any quality assurance or regulatory issues that occurred during the past year, summary of Adverse Events and Serious Adverse Events, and any actions or changes regarding the protocol.

We will use the Research Electronic Data Capture (REDCap) online database management system that the University of Missouri provides. In this secure network, we will store all study data, data collection instruments, schedule follow-up assessments, monitor enrollment, and manage secure storage. The University of Missouri School of Medicine Bioinformatics Department will provide database management technical support for the data-capture system. Data will be collected via an e-mailed link to all participants with instructions for them to complete the surveys. Based on entered data, the Data Manager will produce reports of apparent data discrepancies and missing data. Data concerns will be addressed through the Data/statistical team and reported to the Steering Committee. Larger concerns with the protocols may be forwarded to the full team or institutional committees depending on their severity. Intervention fidelity will be monitored monthly by Drs. [name] and [name]. Data quality will be monitored by random inspection of the completed forms by the Data Manager, and any problems detected will be discussed with the Steering Committee.

During screening, study applicants will be assessed to determine their eligibility and safety of their participation in this study. We will use the University of Missouri Institutional Review Board (IRB) definition of serious adverse events. The IRB understands that this definition is unusual in hospice, where deaths are not considered an adverse event because all hospice patients are expected to die. Any adverse event, whether or not related to the study intervention, will be reported to the IRB.

All personnel involved with this study will receive appropriate IRB training, including for human subjects training and HIPAA. The PIs will maintain certification of this training.

Responsibilities for data monitoring and safety are outlined below:

- Co- Principal Investigators: The Co- PIs will supervise the study personnel. They will monitor the day-to-day implementation of the intervention and all data collection. They will be in regular contact with each hospice and readily available to identify safety concerns and solve problems. Adverse events that are reported to or observed by the Co-PIs will be reported to the Total Research Team, University of Missouri IRB, and Health Sciences Data Monitoring Safety Board as requested.

- Steering Committee: The research team includes all faculty Co-Is and research staff. Research staff will report all observations, concerns or issues related to the safety of participants or the collection of data. The Co-PIs and Research Specialists will meet weekly to review the status of the intervention, identify problems in the study.
- Each committee meets regularly and reports to the Steering committee any data or safety concerns. All members of the research team are responsible for assuring that any adverse events are reported to the University of Missouri IRB.

## XI. Multiple Sites

As we have done in our past clinical trials, all IRB approvals are handled through one institutional IRB. This success has been contingent upon appropriate IRB training by all Co-Is and research staff credentialed through CITI IRB training with customized institutional modules. The IRB application will be submitted to the University of Missouri Institutional Review Board (MU IRB), which will serve as the single IRB with oversight of the study. Drs. [name] and [name], Co- Principal Investigators, will be responsible for all communication between sites and will ensure appropriate IRB approvals are in place prior to the initiation of research activities. MU IRB will maintain records of authorization and of all pertinent communication.

# **Caregiver Speaks Data Analysis Plan**

**January 5, 2019**

**NCT04103580**

## Data Analysis

### Statistical Assumptions

We will routinely test assumptions of linearity, independence and homoskedasticity by calculating and plotting residuals and Cook's distance for all models. Where data are missing, we will substitute the mode for categorical data and the median for continuous data, given that <0.5% of data were missing for any measure in our preliminary trial. If the proportion of missing data is higher, we will use multiple imputation. In the analysis for H1a, we will use the final measure provided by caregiver before patient death, and for H1b we will use the final measure during bereavement. Because the sample size is relatively large, we expect that known and unknown confounders will be distributed evenly among the two groups. We acknowledge that this study is not powered to detect small interaction effects. Additional confounders will only be introduced as covariates if we find evidence of imbalance between groups at baseline.

We will test whether randomization created balanced groups by comparing baseline measures and demographic characteristics, using chi-square or t-test analysis for categorical or continuous variables, respectively. Variables that differ significantly between groups will be included in regression models as potential confounders. To compare outcomes for our hypotheses, we will use the last available measure post-baseline and prior to death or the end of the study and last measure during bereavement. This is a last-observation analysis.

Carpenter and Kenward argue that, in such analyses, time to this event should be taken into account. Therefore, we will include time from study enrollment to the last observation as a covariate. We will report estimates with 95% confidence intervals. To draw inferences from our study to the likely benefit to an equivalent population where the intervention under trial is a model of service delivery, all analyses of outcomes will be by intention-to-treat. The intention-to-treat analysis, consistent with the objectives of a pragmatic trial, will minimize the influence of "informative missingness" of the data and preserve groups' comparability.

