**Table 2: Aims, Hypotheses, and Associated Measures**

*Pre-bereavement measures collected at baseline, 14, 30, 90, and 150 days (follow-up data collection post 150 days will occur every 6 weeks until participant transitions to bereavement). Post-death measures collected at transition, 14, 30, 90, 150 and 180 days. During study wind down, participants will complete their final data collection measure based on where they are at in the intervention (e.g., if a participant is on day 90 of 150, they will complete day 90 survey as their final measure).*

Specific Aim	Hypotheses (H) and Research Questions (RQ)	Instruments and Variables	Description
Aim 1: Determine the efficacy of the Caregiver Speaks intervention in reducing depression and anxiety among hospice family caregivers of PLWD.	RQ1: What is the effect of the Caregiver Speaks intervention on caregivers' depression, anxiety (outcomes of interest)? H1a: Family caregivers receiving the intervention will	Primary Outcome: Depression Patient Health Questionnaire (PHQ-9) Secondary Outcome: Anxiety Generalized	PHQ-9: a 9-item screening tool and severity measure for depressive mood.  Internal Consistency: .87 

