### **Data Analysis Plan:**

**Statistical Assumptions.** We will examine linearity and homoskedasticity by calculating and plotting residuals and Cook's distance for all models. Where data are missing, we will use the Last Observation Carried Forward (LOCF) missing data imputation technique, given that < 30% of data were missing for any particular subject in our prior work. If the proportion of missing data is higher, we will use regression based multiple imputation. Little's MCAR test (missing completely at random) will be used to test that missingness is in no way related to the intervention. Because the sample size is relatively large, we expect that known and unknown confounders will be distributed evenly among the two randomized groups. Additional confounders will only be introduced as covariates if we find evidence of imbalance between groups at baseline. We acknowledge that this study is not powered to detect small interaction effects.

We will test whether randomization created balanced groups by comparing baseline measures and demographic characteristics, using chi-square or t-test analysis for categorical or continuous variables, respectively. Variables that differ significantly between groups will be included in regression models as potential confounders. We will include time from study enrollment to the last observation as a covariate, as well as hospice agency. We will report estimates with 95% confidence intervals. To draw inferences from our study for the likely benefit to an equivalent population, where the intervention under trial is a model of service delivery, all analyses of outcomes will be by intention-to-treat. The intention-to-treat analysis, consistent with the objectives of a pragmatic trial, will minimize the influence of "informative missingness" of the data and preserve groups' comparability.

**Statistical Analysis.** H1a: Family caregivers receiving the intervention will report lower levels of depression and anxiety (outcomes of interest), which is facilitated by higher social support (mediating variable) than those in the control group during active caregiving.

H1b: Family caregivers receiving the intervention will report lower levels of depression and anxiety (outcomes of interest), which is facilitated by higher social support (mediating variable) than those in the control group during bereavement.

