**Subgroup Analysis.** We will analyze several subgroups to identify unique attributes that might influence outcomes. Our subgroups are 1) hospice agency, to reflect different organizational structures, 2) older age, gender, race & ethnicity, which might influence use or understanding of Facebook, 3) Caregiver relationship to and residence with the patient, which could affect the meaning and amount of burden and 4) Time from enrollment to last observation, which reflects intervention dose, and 5), co-morbidities in patients, which may impact caregiving outcomes.

**Qualitative Analysis.** See Table 3 (below) for a detailed qualitative analysis plan. We will enter all photos, qualitative Facebook data, and transcribed interviews into qualitative coding software (Dedoose) for triangulation (use of multiple data sources to ensure a rich and robust dataset) and thematic analysis.

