### Statistical Analysis

**H1a:** Family caregivers receiving the Caregiver Speaks intervention will report lower levels of depression and anxiety compared to those in the control group during active caregiving.

**H1b:** Family caregivers receiving the intervention will report lower levels of depression and anxiety compared to those in the control group during bereavement.

**H2:** Bereaved family caregivers receiving the intervention will report lower levels of grief intensity compared to those in the control group.

We will examine differences between longitudinal profiles of the two study groups for each of the outcomes (PHQ-9, GAD-7, social support, & grief intensity). We will use mixed (hierarchical) models with repeated outcome measures nested within participants (see model below). This will allow us to draw inferences about how our outcome measures (PHQ-9, GAD-7 & grief intensity) change over time (slope) between the two study groups. Mixed models are able to accommodate differing numbers of measurements at varying time intervals for participants. Additionally, we will examine how social support mediates our outcomes of interest (depression, anxiety, and grief intensity). As described above, we will also include covariates where indicated.

**Last post-baseline measure =  $\beta_0 + \beta_1[\text{study group}] + \beta_2[\text{baseline measure}] + \beta_3[\text{time since enrollment}]$**

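### For the bereavement outcomes (H1b, H2) the only stated time covariate runs from enrolment, so it adjusts only partly for how long the caregiver has been bereaved

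*SAP*

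**What the plan says.** The SAP (Statistical Assumptions) describes a last-observation analysis. For the bereavement hypothesis, "for H1b we will use the final measure during bereavement". It accepts that "in such analyses, time to this event should be taken into account" and meets that need with one covariate: "Therefore, we will include time from study enrollment to the last observation as a covariate".

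Under Statistical Analysis the SAP lists H1a, H1b and H2 together and prints one regression for them. Its only time term is "time since enrollment".

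The protocol (Data Analysis Plan, Statistical Assumptions) carries the same rule: "We will include time from study enrollment to the last observation as a covariate, as well as hospice agency". Its subgroup paragraph gives the variable another meaning: "Time from enrollment to last observation, which reflects intervention dose".

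The survey schedule in the protocol's Table 2 uses two clocks. Before the death, "follow-up data collection post 150 days will occur every 6 weeks until participant transitions to bereavement". Afterwards, "Post-death measures collected at transition, 14, 30, 90, 150 and 180 days".

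The protocol's mixed model for H1a and H1b, with a similar one for H2, has a slope on visit time t_ij. It does not say when t_ij is zero.

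**The concern.** Grief intensity is measured only in bereaved caregivers, and the bereavement surveys are timed from the death. The quantity that places a caregiver in the course of grief is therefore time since death. The stated covariate adds to it a pre-death period that can be long and differs between caregivers, so equal covariate values can hide very different stages. A value of 200 days fits a death on day 20 followed by the day-180 survey, and equally a death on day 186 followed by the day-14 survey. A caregiver bereaved on day 300 whose last survey is at day 14 (total 314) even counts as later than the day-180 completer with a total of 200.

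The covariate is there for the case of unequal last-measure times. If one arm tends to stop earlier in bereavement, its caregivers are more recently bereaved when last measured and may look worse for that reason alone. At stake is how much of that distortion the stated adjustment leaves in the Aim 2 comparison and in the bereavement half of Aim 1.

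**Working it through.** **No planned figure to reproduce.** The documents give no rate of change in grief, no length of hospice stay and no distribution of last-survey times. Everything numerical below except the visit days, the 234 per arm and the 30% attrition is an assumption.

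**Formula.** Let L be days from enrolment to death, B days from death to the last survey, and T = L + B the SAP covariate. Suppose the score falls linearly at rate r per day of bereavement, there is no true arm effect, and L is independent of B with the same distribution in both arms. Let d be the difference between arms in mean B, and let v_B and v_L be the within-arm variances of B and L (v_B averaged over the arms). Then:

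- Unadjusted spurious difference: r × d.
- Adjusted for T: the coefficient on T is −r × v_B / (v_B + v_L), so r × d × v_L / (v_B + v_L) remains.
- Adjusted for B: zero.

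If d = 0, all three are zero. With L exponential with mean m, v_L = m².

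**Scenario 1: 40% (control) versus 58% (intervention) stop before day 180.** Last surveys at days 14/30/90/150/180 have probabilities .08/.08/.12/.12/.60 in control and .16/.16/.14/.12/.42 in intervention.

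- Mean B: 140.3 and 113.2 days, so d = 27.1.
- Variance of B: 3,510 and 4,794, so v_B = 4,152.
- With r = 1/30 point per day, unadjusted bias = 27.1 / 30 = 0.90 points.

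**Scenario 2: 25% versus 35% stop early, averaging the protocol's 30% attrition.** Early stoppers in both arms have the control mix of scenario 1 (.2/.2/.3/.3 over days 14/30/90/150).

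- Mean early survey day: 80.8, so d = 0.10 × (180 − 80.8) = 9.9 days.
- Variance of B: 2,563 and 3,243, so v_B = 2,903.
- Unadjusted bias = 9.9 / 30 = 0.33 points.

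| Mean enrolment-to-death time (days) | Scenario 1: share left | Scenario 1: points left of 0.90 | Scenario 2: share left | Scenario 2: points left of 0.33 |
|---|---|---|---|---|
| 20 | 9% | 0.08 | 12% | 0.04 |
| 30 | 18% | 0.16 | 24% | 0.08 |
| 60 | 46% | 0.42 | 55% | 0.18 |
| 120 | 78% | 0.70 | 83% | 0.28 |
| 200 | 91% | 0.82 | 93% | 0.31 |

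For example, at mean 60 in scenario 1: 3,600 / (3,600 + 4,152) = 0.464, and 0.464 × 0.90 = 0.42.

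**Different inputs, same pattern.** Take a fall of 3 points over 180 days, 20% versus 40% stopping early, and early stoppers spread evenly over days 0, 14, 30, 90 and 150. The unadjusted bias is 0.41 points. Adjusting for time since enrolment leaves 0.08, 0.20, 0.28, 0.35 and 0.38 at means of 30, 60, 90, 150 and 240 days. Adjusting for time since death leaves 0.00.

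**Yardstick.** Losing 30% of 234 leaves about 163 per arm. With an assumed SD of 10, the standard error of an arm difference is 10 × √(2/163) = 1.1 points. Every value above is below that.

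**The case against.** Four points can be made for the plan.

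1. *The covariate does adjust.* Time since enrolment contains time since death. With a mean of 20 to 30 days before death it removes about 76% to 91% of the bias in the two scenarios. This stands. A reader might infer that the adjustment does nothing for stage of grief, or that most of the bias always remains. The first is wrong, and the second depends on a length of stay that the documents do not give.

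2. *No bias without unequal timing.* This also stands. Wind-down applies to both arms and, with 1:1 randomisation in blocks within site, is not expected to differ between them. Contact does differ: the added one-week call and the two bereavement interviews are for the intervention group only. Timing could therefore differ, but nothing in the documents shows that it will. A reader might infer that the Aim 2 result will be biased, and the text does not support that.

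3. *The mixed model handles time through t_ij.* This stands in part. In the protocol, the last-observation equation appears only under H1c, and a visit-time slope counted from the death would carry the adjustment. But the origin of t_ij is not defined, the protocol still adds the enrolment covariate, and the model that the SAP prints for H1b and H2 is the last-observation regression.

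4. *The replacement is not clean.* Days from death to last survey is determined after randomisation, and the zero bias above assumes that dropout is unrelated to grief. In simulations where intervention-arm dropout depended on underlying grief (assumed SD 7, mean 120 days before death), adjusting for days since death gave spurious differences of −0.22 and −0.36 points. The current covariate gave +0.44 and +0.42. Both are affected, which is a reason for a sensitivity analysis rather than for keeping the enrolment clock.

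**Conclusion.** The point holds in a limited form. For H1b and H2 the documents name one time covariate, counted from enrolment, and it mixes the length of the pre-death period with time since death. It therefore corrects only partly when last bereavement measures fall at different times since death in the two arms. If timing is equal, the cost is some precision and a covariate that is hard to interpret.

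Under the stated assumptions the remaining bias is 0.04 to 0.31 points with early stopping near the planned attrition, and 0.08 to 0.82 points with heavier and more unequal stopping. It grows with the pre-death period and in proportion to the rate of decline in grief. It stays below one standard error, so this is not a reason to call the bereavement analyses invalid. The change is worth making because the SAP itself sets out to account for the time of the last measure, and for these outcomes a more suitable clock is available at almost no cost.

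**What to change.** Amend the SAP (Statistical Assumptions and the equation under Statistical Analysis) and the protocol's Data Analysis Plan:

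- **H1b and H2:** replace time since enrolment with days from the patient's death to the survey analysed, and add enrolment-to-death time as a separate term.
- **Mixed model:** state that t_ij is measured from the death for the bereavement outcomes.
- **H1a:** keep time since enrolment.
- **Sensitivity analysis:** alongside the last-observation result, report the repeated-measures estimate or an analysis without the last-observation time covariate.

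The cost is wording, one extra model term and one extra reported analysis. The date of death is already needed to schedule the post-death surveys. The new covariate, like the present one, arises after randomisation and can mislead if dropout depends on outcome, so the sensitivity analysis belongs to the change.

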### Statistical Analysis

**H1a:** Family caregivers receiving the Caregiver Speaks intervention will report lower levels of depression and anxiety compared to those in the control group during active caregiving.

**H1b:** Family caregivers receiving the intervention will report lower levels of depression and anxiety compared to those in the control group during bereavement.

**H2:** Bereaved family caregivers receiving the intervention will report lower levels of grief intensity compared to those in the control group.

We will examine differences between longitudinal profiles of the two study groups for each of the outcomes (PHQ-9, GAD-7, social support, & grief intensity). We will use mixed (hierarchical) models with repeated outcome measures nested within participants (see model below). This will allow us to draw inferences about how our outcome measures (PHQ-9, GAD-7 & grief intensity) change over time (slope) between the two study groups. Mixed models are able to accommodate differing numbers of measurements at varying time intervals for participants. Additionally, we will examine how social support mediates our outcomes of interest (depression, anxiety, and grief intensity). As described above, we will also include covariates where indicated.

**Last post-baseline measure =  $\beta_0 + \beta_1[\text{study group}] + \beta_2[\text{baseline measure}] + \beta_3[\text{time since enrollment}]$**

